### Exclusion Criteria

The following exclusion criterion will be considered in all the cohorts:

[figure not shown]
- For each AESI, subjects (in any matched cohort) who had a specific AESI (Table 3) during the look-back period before the index date will be excluded from the cohort for the analysis of that specific AESI, but not from the cohorts for analysis of other AESIs.
  - If a subject had a specific AESI between the index date and the start of the risk window or had any censoring criteria within this time period, the subject will be excluded from the analysis of that specific AESI.

The number of subjects in the *all AZD1222 vaccinated first dose population* and in the *all mRNA vaccinated first dose population* excluded because they had no matches will be described. Similarly, the number of subjects in the initial pool of potential concurrent

unvaccinated comparators and historical comparators that fulfil the inclusion criteria but are excluded because they had no matches will be described.

In the analysis of a specific AESI, if a subject in the *AZD1222 matched cohort* is excluded due to having a prior history of that specific AESI, all its matched subjects will also be excluded from that analysis. Analogously, if the matched subject in the *concurrent unvaccinated comparator* matched cohort or in the *active comparator* matched cohort or in the *historical comparator* matched cohort is excluded, then the corresponding subject in the *AZD1222 matched cohort* will also be excluded from the analysis of that specific AESI.

**Figure 2** Assembly of Study Cohorts

[figure not shown]

Note: The process illustrated here will be conducted separately in each data source. Index date refers to the date of the first dose of AZD1222 for each vaccinee and for each unvaccinated comparator subject (minus 3 or 4 years for each matched historical control) or the date of the first dose of an mRNA vaccine for each active comparator subject. Subjects in the concurrent unvaccinated cohort will be allowed to enter the AZD1222 or the active comparator cohort if they later fulfil specific cohort entry criteria.

Note that the comparative analysis between AZD1222 and active comparator cohorts will be conducted among vaccinees who have received 2 doses. COVID-19, coronavirus disease 2019; SCRI, self-controlled risk interval.

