j Based on Serazin et al (2021).

k Clean interval refers to the look-back period before cohort entry during which no AESI was observed. Unless indicated otherwise, the interval duration is based on the clinical judgement of the research team.

Note: Risk window definitions may evolve during the course of the study as more knowledge is gathered about individual AESIs.

AESI, adverse event of special interest; ARDS, acute respiratory distress syndrome; COVID-19, coronavirus disease 2019; FDA, Food and Drug Administration; IOM, Institute of Medicine; ME, myalgic encephalitis; PVFS, postviral fatigue syndrome; SCRI, self-controlled risk interval; TTS, thrombosis with thrombocytopenia syndrome.

Outcomes will be identified using algorithms based on codes for diagnoses, procedures, and treatments in electronic data, and they will be defined uniformly across the data sources to the fullest extent possible. Operational case definitions from the ACCESS project ([https://drive.google.com/drive/folders/1Y\\_3cuGRN1g-jBv2ec1fC0aYcpxEjtrY9](https://drive.google.com/drive/folders/1Y_3cuGRN1g-jBv2ec1fC0aYcpxEjtrY9)) will be

implemented for the AESIs for which they have been developed. The SAP will include detailed information on codes and algorithms.

If feasible, algorithms to identify selected AESIs will be validated in a sample of cases based on manual review of electronic records or chart abstraction conducted by clinicians blinded to COVID-19 vaccine exposure. If validation is performed, certainty of an event diagnosis will be classified against existing and as-yet developed standardised definitions such as those created by the Brighton Collaboration.

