### 9.3.2.1 Thrombosis With Thrombocytopenia Syndrome

As previously noted, case definitions will be specified in the SAP, however, given its clinical importance, additional details for defining TTS are provided here. As of May 2021, no TTS standard case definition has been accepted for use by all countries ([Brighton Collaboration 2021b](#)). The Brighton Collaboration interim case definition for TTS (version 10.16.2, 18 May 2021) defines TTS as “Any patient presenting with both acute venous or arterial thrombosis AND new-onset thrombocytopenia (TCP)” [as confirmed by both the Brighton Case Definitions for thrombocytopenia and thrombosis ([Brighton Collaboration 2021a](#), [Wise et al 2007](#))]. The Brighton Collaboration case definition for TCP ([Wise et al 2007](#)) requires evidence of a platelet count of less than  $150,000/\mu\text{L}^3$ .

[figure not shown]
Because laboratory measurements of platelet counts are not expected to be available for most proposed data sources, the case definition of TTS for the current study has been adapted to qualify TCP based on a diagnosis code. In addition, diagnoses that qualify for thrombosis do not include acute myocardial infarction (AMI) or stroke, which is consistent with the May 2021 Centers for Disease Control and Prevention (CDC) working case definition for TTS following COVID-19 vaccination ([CDC 2021](#)). It should be emphasised that the proposed case definition for this study is provisional and subject to change as the Brighton case definition evolves and in response to findings from validation exercises. Because the concept of “thrombosis” also includes embolic events, for purposes of the case definition, the concept has been relabeled “thromboembolic event” (TE).

The working TTS case definition for this study requires:

- A new qualifying TE (defined below) AND
- A new diagnosis of TCP (or laboratory evidence of the same, where available) that is made from 10 days before and up to 10 days after that event (<https://zenodo.org/record/5255870#.Yx8KBHZBxPZ>) ([Burn et al 2022](#))

[Figure 5](#) shows the look-back (“washout”) periods proposed to define “new” diagnoses.

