**Figure 5 Time Windows to Define Thrombosis With Thrombocytopenia Syndrome**

dx, diagnosis.

Thromboembolic events will include new diagnoses of embolism or deep vein thrombosis (DVT) (including splanchnic, intracranial, limb locations) or thromboembolism. According to the working case definition, infarctions (including myocardial and cerebral) and stroke will not qualify as a TE in the main analysis but will be included in a sensitivity analysis in order to evaluate the potential effect of AZD1222 on arterial thrombosis and thromboembolisms. In addition to evaluating TEs overall, it is proposed to evaluate DVT outcomes separately by location of the event into central venous sinus thrombosis, limb thrombosis, and splanchnic area thrombosis. In the primary analysis, the risk window for TTS extends from 1 to 42 days after vaccination (or the corresponding index date for the unexposed comparator subject).

Sensitivity analyses will be conducted:

- Including the TTS definition described previously but adding infarctions (including myocardial and cerebral) and stroke (Interim Report 2 and final study report)
- Using alternative risk windows of 1 to 14 days, 1 to 21 days, and 1 to 28 days after the index date (final study report)

Both TE and TCP will be ascertained using codes for diagnoses, procedures, and treatments in electronic data that are also under development within the studies conducted under the VAC4EU framework.

Identification of the clinical concerns “Thromboses without thrombocytopenia” and “Thrombocytopenia without thrombosis” will follow a similar logic.

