### 9.3.2.2 Thrombocytopenia With Bleeding

As of June 2021, there appears to be no standard case definition to study thrombocytopenia with bleeding following vaccination. The approach proposed to identify this outcome in automated data will follow the same approach used for TTS (Section 9.3.2.1), using bleeding instead of TE to anchor the search. It will use the same look-back period to define “new” diagnoses (Figure 5). Briefly, the working case definition for thrombocytopenia with bleeding for this study requires 2 components:

- A new qualifying bleeding event (defined below) AND
- A new diagnosis of TCP (or laboratory evidence of the same, where available) that is made from 10 days before and up to 10 days after that event

Bleeding events will include new diagnoses of clinically significant bleeds in the central nervous system, respiratory tract, gastrointestinal tract, or genitourinary tract, where “clinically significant” means requiring hospitalisation or emergency department care. Both bleeding and TCP will be ascertained using codes for diagnoses, procedures, and treatments in electronic data that are also under development within the studies conducted under the VAC4EU framework. However, as for TTS, definitions and risk window definitions may evolve during the course of the study as more knowledge is gathered about individual AESIs and while definitions are under development within the studies conducted under the VAC4EU framework.

In the primary analysis, the risk window for thrombocytopenia with bleeding extends from 1 to 42 days after vaccination (or the corresponding index date for the unexposed comparator subject). A sensitivity analyses will also evaluate the alternative risk windows of 1 to 28 days, following Pottegård et al (2021). As feasible, cases of TCP with bleeding identified from automated data will be reviewed using the approach outlined for TTS (Section 9.3.2.1.1). Information will be sought about the magnitude of thrombocytopenia (ie, platelet count) and any specific cause of the TCP.

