### 9.7.10 Sensitivity Analyses

For each of the matched cohort populations (ie, AZD1222 cohort with concurrent unvaccinated comparator cohort, AZD1222 cohort with active comparator cohort, and AZD1222 cohort with historical comparator cohort), the following sensitivity analyses will be conducted analogously to the main analysis:

- The direct effect of vaccination with AZD1222 on the AESIs will be estimated, excluding subjects with prior COVID-19 diagnosis and thus censoring their follow-up at the occurrence of a COVID-19 diagnosis.
- The effect of partial censoring within matched pairs on the AESIs will be estimated by censoring both members of a matched pair when one member is censored.
- For thrombocytopaenia with bleeding, an alternative risk window of 1 to 28 days at the index date (instead of the 1 to 42 days in the primary analysis) will be assessed.
- For TTS; 3 alternative risk windows of 1 to 14 days, 1 to 21 days, and 1 to 28 days after the index date (instead of 1 to 42 days in the primary analysis) will be assessed.
- For TTS; an alternative definition of the outcome will include not only thrombocytopaenia with venous thromboembolisms but also thrombocytopaenia with AMI or stroke. The risk window between thrombocytopaenia and AMI or stroke will be the same as the one used for venous thromboembolism, ie, 10 days.
- For TTS; AESI cases will be restricted to confirmed cases (ie, excluding cases that could not be validated). The resulting positive predictive values (PPVs) will be used to correct the observed PPV from the main results. This analysis will be performed depending on the total number of outcomes that will be validated (as detailed in Section 9.3.2.1.1).
- In CPRD, a sensitivity analysis using hospital data to assess the AESIs will be performed at the time of the final analysis. However, depending on the duration of the lag time for hospital data at the time of the final analysis, the analysis using hospital data may be considered as the primary analysis.

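### TTS and thrombocytopenia with bleeding: as the text stands, a thrombocytopenia record dated before vaccination can complete a case whose other component falls on days 1 to 9

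*Protocol*

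**What the plan says.** Section 9.3.2.1 builds a TTS case from a new qualifying thromboembolic event and a new thrombocytopenia diagnosis (or laboratory evidence of it) "that is made from 10 days before and up to 10 days after that event". Section 9.3.2.2 repeats the rule for thrombocytopenia with bleeding, "using bleeding instead of TE to anchor the search". Both sections refer to Figure 5 for the look-back that makes a diagnosis new.

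The risk windows are counted from vaccination or the assigned index date. For TTS: "In the primary analysis, the risk window for TTS extends from 1 to 42 days after vaccination". For the other outcome: "the risk window for thrombocytopenia with bleeding extends from 1 to 42 days after vaccination". Section 9.7.10 adds, for TTS, "3 alternative risk windows of 1 to 14 days, 1 to 21 days, and 1 to 28 days after the index date", a 1-28 day window for thrombocytopenia with bleeding, and a TTS variant that admits AMI and stroke.

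Two further rules bear on the point. The exclusion criteria in 9.2.1.1.3 remove subjects with a prior event of a given AESI from the analysis of that AESI, "but not from the cohorts for analysis of other AESIs". Footnote k to Table 3 puts it the same way: "Clean interval refers to the look-back period before cohort entry during which no AESI was observed". Thrombocytopenia alone, thrombocytopenia with bleeding, and TTS are separate rows in that table. Section 9.2.3.1 censors composite outcomes at whichever component occurs first.

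**The concern.** The spacing rule and the risk window run on different clocks. The spacing rule links the two components to each other; the risk window links the outcome to vaccination. No visible sentence places the thrombocytopenia after the index date. Thrombocytopenia coded on day -5 and a deep vein thrombosis on day +3 therefore satisfy the written case definition, although one defining component was on record before the dose.

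The exclusion rule does not clearly remove this subject. Thrombocytopenia on day -5 is a prior event for the thrombocytopenia analysis, but it is not a prior TTS.

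TTS is one of the safety concerns that led to this study. Cases that began before exposure add background events to both numerator and comparator. They weigh most in the short windows, which look closest to the dose.

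**Working it through.** The plan gives no figure for this, so the check enumerates what the rule permits.

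Inputs: anchor (thromboembolic event or bleed) on day t, with t from 1 to W; thrombocytopenia on any day from t - 10 to t + 10, which is 21 days (9.3.2.1, 9.3.2.2); index date is day 0; W = 42 in the primary analysis, 28, 21 and 14 for the TTS alternatives, and 28 for the bleeding alternative (9.7.10).

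**Which anchor days are exposed.** Thrombocytopenia can precede day 0 only if t - 10 < 0, so t is 1 to 9. That is 9 of 42 anchor days (21%) in the primary window and 9 of 14 (64%) in the shortest.

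**How many day pairs.** For anchor day t there are 10 - t permitted days before day 0. The sum over t = 1 to 9 is 9 + 8 + ... + 1 = 45. Permitted pairs in total are 21 × W.

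| Window | Permitted pairs | Thrombocytopenia strictly before day 0 | Share |
|---|---|---|---|
| 1-42 | 882 | 45 | 5.1% |
| 1-28 | 588 | 45 | 7.7% |
| 1-21 | 441 | 45 | 10.2% |
| 1-14 | 294 | 45 | 15.3% |

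These equal shares of cases only if anchors are uniform over the window and offsets uniform over -10 to +10 days. Both are assumptions. Adding thrombocytopenia on day 0 itself adds one pair for each of t = 1 to 10, giving 55 pairs: 6.2% for 1-42 and 18.7% for 1-14. A day-0 record is not strictly before vaccination, so 45 is the right count for this point.

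**If offsets cluster near zero.** The share is (1/W) × Σ P(offset < -t), summed over t = 1 to W.

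- Triangular weights 11 - |k| for k from -10 to 10 (total 121): the sum is 165/121 = 1.36 days, giving 3.2% (1-42), 4.9% (1-28), 6.5% (1-21) and 9.7% (1-14).
- Weights exp(-|k|/2), mean absolute offset 1.9 days: the sum is 0.56 days, giving 1.3%, 2.0%, 2.6% and 4.0%.

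**Pooling doses.** The main analysis combines time after dose 1 and dose 2 (9.7.6). Thrombocytopenia in the days just before dose 2 normally follows dose 1 and is not pre-vaccination. If every subject had two full, non-overlapping 42-day windows with equal numbers of anchors, the uniform share would fall to 45/(2 × 882) = 2.6%.

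**Effect on the ratio.** Suppose such cases are a share f of background cases, occur equally in both cohorts, and the true ratio for the rest is R. The observed ratio is then f + (1 - f)R. With R = 2 chosen for illustration, f = 0.051 gives 0.051 + 0.949 × 2 = 1.95, and f = 0.153 gives 0.153 + 0.847 × 2 = 1.85. Equal additions cancel in the absolute risk difference.

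**The case against.** The strongest reply is that the documents at hand do not settle whether such cases are counted. Figure 5 defines a new diagnosis and is lost from the extracted text; its washout may run back from the index date, and a lost figure is not a gap in the plan. No sentence says which component dates a TTS event. If the first-component rule in 9.2.3.1 covers TTS, the day -5 / day +3 case is dated before index and falls outside the risk window. Section 9.3.2.1 also calls the definition provisional and leaves case definitions to the SAP.

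Much of this stands, and it rules out saying that pre-vaccination thrombocytopenia is definitely counted. It does not dispose of the point. The first-component rule reads naturally for either/or groupings; TTS needs both components, and the search is built around the thromboembolic event. If the rule does apply to TTS, the sections still need reconciling. The protocol also chose to fix the TTS timing rule itself because of the outcome's clinical importance, so this is more than a detail left for later.

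Expert review (9.3.2.1.1) and the confirmed-case sensitivity analysis (9.7.10) help only in part. Timing of thrombocytopenia against vaccination is not among the data sought, reviewers are blinded to vaccination status where possible, and the sensitivity analysis depends on how many cases are validated.

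A reader might also infer a bias in the vaccine's favour: vaccination is put off after fresh thrombocytopenia, while a comparator is simply assigned the date. The documents give no support for that. The same case rule applies to both cohorts, and the direction of any difference between them is not established.

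**Conclusion.** The point holds in a limited form. Under the visible text, thrombocytopenia recorded before the index date can complete a TTS or thrombocytopenia-with-bleeding case when the other component falls on days 1 to 9, and the AESI-specific exclusion does not clearly prevent it.

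After dose 1, the affected share of permitted day pairs is 5.1% in the primary window and rises to 15.3% in the 1-14 day window if offsets are uniform. It falls to 1.3% and 4.0% with tight clustering, and is lower again once dose-2 windows are pooled. These are shares under assumed offsets, not predictions of case counts.

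The expected consequence is modest dilution of the ratio, greatest in the short windows. The conclusion is conditional on Figure 5 not already imposing an index-based washout.

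**What to change.** Unless Figure 5 already does so, add one sentence to 9.3.2.1 and 9.3.2.2: both components must be dated after the index date, meaning dose 1 for vaccinees and the assigned index date for comparators. Keep the 10-day spacing. Apply the same condition to the AMI/stroke variant in 9.7.10. State which component dates the event, and reconcile that with the first-component censoring rule in 9.2.3.1. If Figure 5 already settles the matter, one sentence in the text saying so is enough.

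Two stronger changes should be avoided. Requiring both components to follow dose 2 in the second window would reject cases whose thrombocytopenia arose after dose 1. A new 365-day exclusion for either component, beyond the existing washout for a new diagnosis, would also drop matched partners under 9.2.1.1.3 and change the analysis population well beyond the defect.

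The cost is one date condition in the outcome algorithm and slightly fewer counted cases. Because the condition also drops day-0 thrombocytopenia, the uniform assumption puts the loss after dose 1 at 55/882 = 6.2% in the primary window and at most 55/294 = 18.7% in the 1-14 day window, less if offsets cluster or doses are pooled.

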**Figure 5 Time Windows to Define Thrombosis With Thrombocytopenia Syndrome**

dx, diagnosis.

Thromboembolic events will include new diagnoses of embolism or deep vein thrombosis (DVT) (including splanchnic, intracranial, limb locations) or thromboembolism. According to the working case definition, infarctions (including myocardial and cerebral) and stroke will not qualify as a TE in the main analysis but will be included in a sensitivity analysis in order to evaluate the potential effect of AZD1222 on arterial thrombosis and thromboembolisms. In addition to evaluating TEs overall, it is proposed to evaluate DVT outcomes separately by location of the event into central venous sinus thrombosis, limb thrombosis, and splanchnic area thrombosis. In the primary analysis, the risk window for TTS extends from 1 to 42 days after vaccination (or the corresponding index date for the unexposed comparator subject).

Sensitivity analyses will be conducted:

- Including the TTS definition described previously but adding infarctions (including myocardial and cerebral) and stroke (Interim Report 2 and final study report)
- Using alternative risk windows of 1 to 14 days, 1 to 21 days, and 1 to 28 days after the index date (final study report)

Both TE and TCP will be ascertained using codes for diagnoses, procedures, and treatments in electronic data that are also under development within the studies conducted under the VAC4EU framework.

Identification of the clinical concerns “Thromboses without thrombocytopenia” and “Thrombocytopenia without thrombosis” will follow a similar logic.

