**Table 3 Adverse Events of Special Interest and Other Safety Concerns**

Adverse event	Suitable for SCRI analysis according to ACCESS protocol template a	Risk interval after index date (days)	Clean look-back interval (days) k
Type III hypersensitivity reactions	No d	1-365 e	365
ARDS	Yes	1-28 j	365
Guillain-Barré syndrome	Yes	1-42 c	365 c
Other peripheral and polyneuropathies	No d	1-42 c	365 c
Multiple sclerosis, and other demyelinating disorders	No d	1-365 e	365 c
Transverse myelitis	Yes	1-90 c	365 c
Optic neuritis/neuromyelitis optica spectrum disorder	Yes	1-42 c	365 c
Encephalitis (including acute disseminated encephalomyelitis)	Yes	1-42 b	183 c
Myasthenia gravis	No d	1-365 e	365
Bell's palsy	Yes	1-42 c	365 c
Generalised convulsions	Yes	0-14 c	365
Narcolepsy	No	1-42 c	365 c
Myocarditis/pericarditis	Yes	1-42 c	365 c
Postural orthostatic tachycardia syndrome	No d	1-42 b	365 c
Myocardial infarction	Yes	1-28 c	365 c
Acute cardiac injury including microangiopathy, cardiogenic shock, and heart failure	No f	1-90 e	365
Stress cardiomyopathy	No f	1-42	365
Thrombocytopenia	Yes	1-42 b	365 c
Thrombocytopenia with associated bleeding	No d	1-42 g	365 c
Thrombosis (embolic and thrombotic events) without thrombocytopenia	Yes	1-42 c	365 c
Thrombosis with thrombocytopenia syndrome	No d	1-42 g	365
Capillary leak syndrome	No d	1-365 e	365
Acute kidney injury	Yes	1-14 b	365
Acute liver injury	Yes	1-14 b	365
Acute pancreatitis	No d	1-365 e	365

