The PRAC AR for Interim Report 1 (7 July 2022) requested that the MAH discuss the need for additional data sources. As per results from this Interim Report 1, 5.8 million subjects included in the study have received at least one dose of AZD1222. The number of AZD1222 vaccinees and data sources included in the current study at this time is considered acceptable for the purpose of interpreting findings as continuous measures that are estimated with varying degrees of precision ([Rothman and Greenland 2018](#)). Therefore, no additional data sources are considered necessary.

**Table 5 Probability That the Upper 95% Confidence Limit of the Observed IRR Will Be Below 1.5, 2, 2.5, and 3 for Various Study Sizes of Vaccinated Subjects, Assuming That the True RR is 1 and the Ratio of Vaccinated-to-Concurrent Unvaccinated Person-time is 3 to 1**

Adverse event (duration of risk interval after each dose)	Estimated background rate per 100,000 PY	People vaccinated	Upper confidence limit of IRR			
			1.5	2.0	2.5	3.0
Anaphylaxis (VAC4EU 2021, Willame et al 2021)	6	1,000,000	0.04	0.05	0.07	0.08
(3 days)	6	2,000,000	0.05	0.07	0.09	0.12
	6	3,000,000	0.05	0.09	0.12	0.16
	6	4,000,000	0.06	0.10	0.15	0.19
	6	5,000,000	0.07	0.12	0.17	0.23
GBS (VAC4EU 2021, Willame et al 2021)	2	1,000,000	0.06	0.11	0.16	0.22
(42 days)	2	2,000,000	0.09	0.18	0.28	0.38
	2	3,000,000	0.11	0.25	0.40	0.53
	2	4,000,000	0.14	0.32	0.50	0.65
	2	5,000,000	0.16	0.38	0.59	0.75
Bell's palsy (Morales et al 2013) (42 days)	38	1,000,000	0.47	0.90	0.99	1.00
VTE a (Heit 2015) (42 days)	100	1,000,000	0.87	1.00	1.00	1.00

a This adverse event is a constituent of the composite AESI “thrombosis.”

Note: Calculations assume a true IRR of 1.0 and a ratio of 1-to-4 exposed to unexposed person-years. Calculations also assume that each person contributes 6 days of follow-up for anaphylaxis (3-day risk interval x 2 doses), 56 days for stroke (28-day risk interval x 2 doses), and 84 days (42-day risk interval x 2 doses) for all other adverse events (Rothman and Greenland 2018). Calculations follow the method of Rothman and Greenland (2018).

AESI, adverse event of special interest; GBS, Guillain-Barré syndrome; IRR, incidence rate ratio; PY, person-years; RR, risk ratio; VAC4EU, Vaccine monitoring Collaboration for Europe; VTE, venous thromboembolism.

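### On the natural reading, stroke without thrombocytopenia is not an event in any listed AESI analysis, and the study-size notes give stroke a risk window that nothing else in the protocol uses

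*Protocol*

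**What the plan says.** Section 9.3.2.1 of the protocol, on thrombosis with thrombocytopenia syndrome (TTS), states that "diagnoses that qualify for thrombosis do not include acute myocardial infarction (AMI) or stroke". Below Figure 5 it repeats that "infarctions (including myocardial and cerebral) and stroke will not qualify as a TE in the main analysis", and admits these events only to a sensitivity analysis meant to evaluate an effect on arterial thrombosis and thromboembolism. The same section closes with: "Identification of the clinical concerns “Thromboses without thrombocytopenia” and “Thrombocytopenia without thrombosis” will follow a similar logic".

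Table 3 (section 9.3.2) lists 37 outcomes. One is "Thrombosis (embolic and thrombotic events) without thrombocytopenia", with a risk interval of 1-42 days. Myocardial infarction has a separate row at 1-28 days. There is no row for stroke or cerebral infarction.

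Section 9.7.10 defines the alternative TTS outcome as "not only thrombocytopaenia with venous thromboembolisms but also thrombocytopaenia with AMI or stroke", with the same 10-day limit between the two components.

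The notes to Tables 5 and 6 (section 9.5) give the follow-up assumed per person, including "56 days for stroke (28-day risk interval x 2 doses"). Neither table has a stroke row.

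**The concern.** Thrombosis is among the safety concerns that section 7 takes from the EU risk management plan. If the TTS exclusion carries over to thrombosis without thrombocytopenia, a vaccinee with a cerebral infarction and a normal platelet count is an event in none of the 37 outcomes, except possibly as a sudden death if fatal within days 0-6. Excluding myocardial infarction costs nothing, because it is analysed in its own right. Excluding stroke has no such backstop.

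Two things are at stake. A null result for an outcome labelled as covering embolic and thrombotic events could be read as reassurance about stroke that the analysis does not supply. And the sensitivity analysis said to address arterial thrombosis sees only arterial events paired with thrombocytopenia, which is a different and much narrower question.

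**Working it through.** **1. Every place where stroke could count as an outcome**

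| Place | Does stroke without thrombocytopenia count? |
|---|---|
| TTS, main analysis (9.3.2.1) | No: stroke is excluded and thrombocytopenia is required |
| TTS, sensitivity version (9.3.2.1, 9.7.10) | No: stroke is admitted, but thrombocytopenia within 10 days is required |
| Thrombosis without thrombocytopenia (Table 3) | Not if the TTS logic carries over its list of qualifying events; members are not listed beyond VTE |
| Myocardial infarction (Table 3) | No: a different event |
| Thrombocytopenia with bleeding (9.3.2.2) | No: central nervous system bleeds count only with thrombocytopenia |
| Cerebrovascular disease (Annex Tables 2 and 3) | No: subgroup indicator and covariate only |

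**2. Which windows the study-size tables use**

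The tables follow a precision method. With N vaccinated, d days at risk, rate r and vaccinated-to-comparator person-time ratio k:

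- A1 = N × (d/365.25) × r and A0 = A1/k
- SE = √(1/A1 + 1/A0)
- P(upper limit < U) = Φ(ln U/SE − 1.96)

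Check on Guillain-Barré syndrome in Table 5 (N = 5,000,000, d = 84, r = 2 per 100,000, k = 3, U = 3):

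- A1 = 23.0 and A0 = 7.67
- SE = √(1/23.0 + 1/7.67) = 0.417
- Φ(1.0986/0.417 − 1.96) = 0.750, against 0.75 printed

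All 48 cells of Table 5 reproduce at 3:1 and all 48 of Table 6 at 1:1, with a largest difference of 0.005. The anaphylaxis rows use 6 days and all the others 84. Had 56 days been used, Table 5 at a limit of 1.5 would show 0.71 for VTE (printed 0.87) and 0.34 for Bell's palsy (printed 0.47). No printed row therefore uses the 56-day stroke assumption.

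**3. The two readings**

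- Stroke is outside the thrombosis composite: it has no outcome row and no window in Table 3, so the 28 days in the notes belong to nothing.
- Stroke is inside the composite: its window is 1-42 days, or 84 days over two doses, which contradicts the 56 days in the notes.

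Either way the passages do not agree.

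**4. Illustration of scale**

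The protocol gives no stroke rate, so the rates below are assumptions. Matched vaccinees in Table 4: 3,938,490 + 517,015 + 609,842 + 336,889 + 154,858 = 5,557,094. With two doses and full follow-up, person-years = 5,557,094 × 56/365.25 ≈ 852,000. The probabilities take k = 3 and a true IRR of 1.

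| Assumed rate per 100,000 PY | Expected strokes in vaccinees | P(upper limit < 1.5) | P(upper limit < 1.25) |
|---|---|---|---|
| 50 | 426 | 0.987 | 0.63 |
| 100 | 852 | > 0.99 | 0.90 |
| 200 | 1,704 | > 0.99 | 0.996 |

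Lack of precision would not explain leaving stroke out.

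**The case against.** The strongest reply is that the exclusion is written for the TTS case definition and rests on a TTS working definition from a public health agency. It reaches thrombosis without thrombocytopenia only through the sentence about similar logic, which could mean the look-back and pairing rules rather than the list of qualifying diagnoses. Table 3 words that row broadly, and the footnote to Tables 5 and 6 calls VTE one constituent of the composite, which suggests others. Codes and algorithms are left to the SAP. Intracranial thrombosis and embolism do qualify as thromboembolic events, so only events classed as infarction or stroke drop out. The stroke wording in the notes looks like a leftover: the same Table 5 note gives a 1-to-4 person-time ratio, while the printed values reproduce only at 3:1.

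Much of this stands. A reader might infer that the protocol expressly removes stroke without thrombocytopenia from all analysis. It does not say so; that is the natural reading of several passages together. A reader might also take the notes as proof that stroke was meant to be an outcome with a 28-day window, or as a sign that the study-size figures are wrong. Neither follows, since no printed figure depends on that note.

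What the reply does not remove is the mismatch between the sensitivity analysis and its aim, or the conflict over the window. Both are fixed in this protocol and hold whatever code lists the SAP contains.

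**Conclusion.** The point holds as an inconsistency with a probable gap behind it. On the natural reading, stroke or cerebral infarction without thrombocytopenia is not an event in any listed AESI analysis. Whichever reading is taken, the TTS sensitivity analysis cannot evaluate arterial thrombosis in general, and the stroke window is either unattached or contradictory.

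The expected counts of about 426 to 1,704 rest on assumed rates, two doses for everyone, full follow-up and Table 4 counts that are partly preliminary. They show that stroke could be estimated with useful precision, not that this many events will be lost. No printed study-size value changes.

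**What to change.** Reconcile section 9.3.2.1, Table 3, the notes to Tables 5 and 6, and section 9.7.10 by stating whether stroke and cerebral infarction belong to thrombosis without thrombocytopenia.

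- **If they do:** say so, and align the notes to Tables 5 and 6 with the Table 3 window.
- **If they do not:** analyse stroke/cerebral infarction irrespective of thrombocytopenia, either as its own Table 3 outcome or as a sensitivity version of thrombosis without thrombocytopenia parallel to the TTS one. The sponsor should choose one risk window and use it in both Table 3 and the study-size notes.
- **If stroke is deliberately out of scope:** delete it from the notes, restate the aim of the sensitivity analysis as arterial thrombosis with thrombocytopenia, and say that a null thrombosis result does not cover stroke.

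The cost is small. The stroke codes are already needed for the TTS sensitivity analysis, so the work is protocol and SAP wording plus, at most, one further run of existing programs. The downside is one more outcome beside 37, in a study that already acknowledges the risk of false positives from multiple comparisons (section 9.9.2).
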